#### 4.2 SCIENTIFIC RATIONALE FOR STUDY DESIGN

This is a before-and-after quasi-experimental, mixed-method pilot design with three survey collection points and a post-study semi-structured interview component. This study will be performed with healthy college students to determine the safety, acceptability, and usability of MKit.

The endpoints are common outcomes of interest for studies of technological interventions. These outcomes will be measured throughout the study, to observe changes over time with continued exposure to the intervention. These endpoints are important outcomes, as interventions must be safe, acceptable, and usable to ensure broad scale uptake. MKit is a primary sexual violence prevention intervention focused on healthy relationships. As such, knowledge, attitudes, and experiences of sexual and intimate partner violence victimization and perpetration are outcomes of interest. Though this pilot study is not powered to detect changes in these secondary outcomes, obtaining data for power calculations for a larger study is a key component of this study.

This study compares usual care for the prevention of sexual and intimate partner violence with care as usual plus the intervention. Both groups will receive interventions currently in place, ensuring that standard care is not withheld from any participant. As the intervention under study is intended to supplement and reinforce current primary prevention programming, the study design will measure the acceptability and preliminary efficacy of broad scale-up of the intervention to the broader college campus.

#### 4.3 JUSTIFICATION FOR DOSE

Intervention group participants will have five months to interact with MKit content, as this time period should present sufficient time for meaningful short-term change in the outcomes of interest. Further, the study will run for the duration of the school year, allowing study staff to follow students from the beginning of the school year to the end of the school year as they interact with MKit.

#### 4.4 END OF STUDY DEFINITION

A participant is said to have completed the study if he or she has completed all three surveys, including the baseline, 1-month, and 5-month surveys, shown in the schedule of activities.

## 5 STUDY POPULATION

### 5.1 INCLUSION CRITERIA

For the pilot study, individuals who meet the following criteria will be considered eligible to participate in the study:

1. Currently enrolled as a student at the participating university
2. Participated in Relationship Remix in Fall 2018 as a first-year or transfer student
3. Willing to participate in the study
4. Able to speak and read English

For the semi-structured interviews, individuals who meet the following criteria will be considered eligible to participate in the study:

1. Currently enrolled as a student at the participating university
2. Participated in Relationship Remix in Fall 2018 as a first-year or transfer student
3. Participated in the pilot study
4. Willing to participate in the study
5. Able to speak and read English

### 5.2 EXCLUSION CRITERIA

Not Applicable

### 5.3 LIFESTYLE CONSIDERATIONS

Not Applicable

### 5.4 SCREEN FAILURES

As all participants will be recruited directly from Relationships Remix, a program for currently enrolled University of Michigan students, all participants are exceedingly likely to be eligible for the study given the inclusion criteria.

### 5.5 STRATEGIES FOR RECRUITMENT AND RETENTION

Students from the target sample, first-year University of Michigan college students, will be recruited for the study. Two residence halls (Alice Lloyd and Couzens) at the University of Michigan will be randomized to receive either: (1) the control arm ( $n=150$ ) which will receive usual care only (all incoming students receive three programs about healthy relationships and sexual violence including Haven, Relationship Remix, and Change it Up) or (2) the usual care ( $n=150$ ) described above and the web-based intervention (MKit). We will use cluster-randomization by residence hall (to minimize contamination associated with individual-level randomization of students living in the same residence hall). At the end of the Relationship

Remix program, a brief announcement will be made about the opportunity to participate in a research study about healthy relationships and palm cards will be distributed (see recruitment materials). We will recruit specifically from Relationship Remix to ensure that all experimental and control subjects receive the same primary prevention programming currently in place on campus. Interested students will receive a palm card with a link to either the MKit web-based application (Intervention) with an access code to sign-up for the website, or a link to the baseline consent and Qualtrics survey (Control) without access to the web-based application. At the end of the study, students from each condition will be invited to participate in an in-person semi-structured interview. Students will receive the invitation to participate in the semi-structured interview on the final page of their 5-month follow-up survey. Students who opt to share their email address with the study team at that time will be contacted to set-up an in-person interview based on user status for the intervention (consistent user of MKit, frequent user of MKit, minimal user of MKit) and a diverse group based on gender, race/ethnicity, and age for the control group. Semi-structured interviews will be conducted with participants from both the Control group (n=10) and the Intervention group (n=15).

The Intervention group will receive the usual care described above, as well as access to MKit. They will be encouraged to interact with the web-based application throughout the study. Built-in reminders to the web-based application, an email alert, and a text-message alert (if the participant chooses to share their phone number) remind participants about their goals and encourage retention and continued engagement.

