## 1.2 SCHEMA

## 1.3 SCHEDULE OF ACTIVITIES (SOA)

Procedures	Preparation before recruitment	Baseline	1-month follow-up	5-month follow-up	Post-study semi-structured interviews
Randomization by residence hall	X				
Demographics		X	X	X	
Sexual and Intimate Partner Violence Knowledge		X	X	X	
Self-Efficacy of Protective Behaviors Related to Sexual and Intimate Partner Violence		X	X	X	
Intimate Partner Violence Attitude Scale		X	X	X	
Consensual Sexual Activity		X	X	X	
Sexual Experiences Survey (Victimization and Perpetration)		X	X	X	
Universal Violence Prevention Screening		X	X	X	
System Usability Scale			X	X	
System Acceptability			X	X	
User Data			X	X	
Reaction to content					X
Perceived safety					X
Desirability					X
Willingness for future use					X

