## 6.3 MEASURES TO MINIMIZE BIAS: RANDOMIZATION AND BLINDING

Study subjects will be randomized into one of two groups: 1) Intervention (WebApp and current prevention programming on campus) or 2) Control (current prevention programming on campus only), with 150 students in each group. We will use cluster-randomization by residence hall (to minimize contamination associated with individual-level randomization of students living in the same residence hall).

This study will not involve blinding.

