## 10 SUPPORTING DOCUMENTATION AND OPERATIONAL CONSIDERATIONS

### 10.1 REGULATORY, ETHICAL, AND STUDY OVERSIGHT CONSIDERATIONS

#### 10.1.1 INFORMED CONSENT PROCESS

##### 10.1.1.1 CONSENT/ASSENT AND OTHER INFORMATIONAL DOCUMENTS PROVIDED TO PARTICIPANTS

Consent forms describing in detail the study intervention, study procedures, and risks are given to the participant and electronic documentation of informed consent is required prior to starting intervention/administering study intervention. The following consent materials are submitted with this protocol:

- Pilot Control Group Consent Form
- Pilot Intervention Group Consent Form
- Semi-Structured Interview Consent Form

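### After open hall allocation, arm-specific cards and consent forms let entry differ by arm, and the plan does not say how the baseline-then-app order is enforced or how survey follow-up for the retention comparison is run

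*Combined protocol and SAP*

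**What the plan says.** **Allocation.** The schedule in section 1.3 puts "Randomization by residence hall" in the preparation column, before recruitment. Section 6.3 adds: "This study will not involve blinding". There are two halls, so one per arm (4.1, 5.5).

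**Entry.** At the end of Relationship Remix, "a brief announcement will be made about the opportunity to participate in a research study about healthy relationships". Interested students then receive "a palm card with a link to either the MKit web-based application (Intervention) with an access code to sign-up for the website", or, for controls, "a link to the baseline consent and Qualtrics survey (Control) without access to the web-based application" (5.5). Section 10.1.1.1 lists one consent form for the control group and a "Pilot Intervention Group Consent Form".

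**Order.** Section 4.1 sets consent first, then the baseline survey in both conditions, then the opportunity to use the app. Section 10.1.1.1 says that "electronic documentation of informed consent is required prior to starting intervention/administering study intervention", and 10.1.1.2 puts online consent before the baseline survey.

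**Follow-up.** The baseline measures are repeated in both arms at 1 and 5 months (1.3, 4.1). Section 5.5 describes built-in, email and optional text alerts for the intervention group, which recall students' goals and are meant to support retention and engagement. The 5-month survey ends with an interview invitation: "Students who opt to share their email address with the study team at that time will be contacted to set-up an in-person interview". Section 3 defines retention as the percentage of participants completing the 1- and 5-month surveys, and 9.1 explores the difference between arms.

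**The concern.** When allocation is known before students decide to join, randomising halls does not protect the make-up of the enrolled groups. One hall is offered an app and the other a survey. Students drawn by an app may differ from those willing to answer a survey alone, and knowing the arm may colour the baseline answers.

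Two further gaps bear on the same comparisons. First, a code handed out at recruitment leaves open whether every intervention baseline is answered before the app is seen, and the before-and-after design relies on that. Second, a between-arm retention figure is hard to read when the plan does not say how students are invited to the follow-up surveys or at which step they start to count.

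The secondary objective is to supply retention and efficacy data for power calculations for a later trial. Planning figures shaped by entry or follow-up procedures would carry that distortion forward.

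**Working it through.** The plan gives no figure to reproduce: section 9.2 says that no formal sample size calculation was done, and it states no retention rate. The check is therefore mainly a comparison of sections.

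1. **Is allocation known at entry?** Halls are allocated before recruitment (1.3), without blinding (6.3). The card shows an app sign-up code or a survey link (5.5), and the consent form is specific to the arm (10.1.1.1). The announcement is described only as concerning healthy relationships, but the card and form come before the decision to enrol. So allocation can be inferred at entry.

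2. **Is this prevented elsewhere?** Section 9.4.5 compares baseline characteristics, 9.4.1 and 9.4.3 compare baseline scores between arms, and 7.1 to 7.3 keep the data of students who stop for attrition analyses. These may reveal a difference in what was measured. They do not prevent one.

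3. **Is the order enforced?** Sections 4.1 and 10.1.1 state it: consent, baseline, app. Section 5.5 hands out the code at recruitment. No section says where the intervention arm's survey sits relative to sign-up, or that content stays closed until the survey is submitted. The order is stated; the mechanism is not.

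4. **How are students brought to the follow-up surveys?** The only contacts said to encourage retention are the MKit alerts. No invitation or reminder procedure for the 1- or 5-month survey is described in either arm. For controls, the only point at which contact details are described as collected is the optional email on the last page of the 5-month survey. That comes too late to serve either follow-up. Section 10.1.3 mentions email addresses without saying when they are obtained.

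5. **What is the retention denominator?** Section 4.4 defines completing the study, not entering it. As 5.5 is written, the first step is app sign-up in one arm and consent in the other, so a count of participants could start at different points.

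6. **Which results are touched?** Usability and acceptability are assessed in the intervention group only, and safety and willingness by interview (9.4.2). None of these rests on a between-arm comparison.

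**Illustration with assumed inputs.** The documents give none of these rates. Take n = 150 per arm, two-sided 5% and students treated as independent.

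- *Retention.* Let p1 and p2 be the two completion rates, d = p2 − p1 and p̄ their mean. The chance of nominal significance is Φ{[d − 1.96·√(2p̄(1−p̄)/n)] / √[(p1(1−p1) + p2(1−p2))/n]}. For 70% against 80%: (0.100 − 1.96 × 0.0500)/0.0497 ≈ 0.04, which gives 52%.

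| Assumed control completion | +5 points | +10 points | +15 points |
|---|---|---|---|
| 60% | 14% | 44% | 80% |
| 70% | 16% | 52% | 88% |
| 80% | 21% | 68% | 98% |

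- *Entry.* For a shift of s standard deviations in a score, with no app effect, the chance is about Φ(s·√(n/2) − 1.96), where √(150/2) = 8.66. Shifts of 0.1, 0.2 and 0.3 give 14%, 41% and 74%. A stable shift may cancel in change scores; differences in change or in dropout would not.

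These figures show that modest procedural differences could look like an arm effect. They are not evidence that such differences will occur.

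**The case against.** The strongest reply has four parts.

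- **The order is already stated.** This stands. A reader might infer that the plan allows app use before consent or baseline. Sections 4.1 and 10.1.1 say otherwise, and a link with a sign-up code need not open any content. Only the enforcing step is undescribed.
- **The retention contrast rests on silence.** This largely stands. A reader might infer that controls will be followed up less. The documents do not show that: survey invitations are undescribed in both arms, and the alerts are partly the intervention itself. A reader might also point to the 15 extra items (10 usability, 5 acceptability) in the intervention arm's follow-up surveys. Those items ask about MKit, and nothing in the documents links them to lower completion, so no weight is placed on them.
- **Other papers may answer it.** The recruitment materials (cited in 5.5), the consent forms and the Manual of Procedures (named in 10.1.10) were not supplied and may describe the flow, the invitations or the card wording.
- **It is a pilot.** The plan calls itself quasi-experimental (4.1, 4.2), says that it is not powered for the outcome measures (9.4.1), and names no between-arm test of retention in 9.4. This stands and limits the severity.

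What survives is that entry differs visibly by arm under the plan as written, and that the steps governing code release, survey follow-up and the retention denominator are unspecified.

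**Conclusion.** The point holds as a low-severity, inexpensive improvement. Following section 5.5 as written, enrolment and baseline answers can differ by arm, and the later baseline and attrition analyses could only describe this. The size and direction of any bias are unknown, and the illustrative percentages depend wholly on assumed rates and independent students.

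The consequence is confined to the secondary, exploratory between-arm comparisons and the planning figures taken from them. The primary endpoints are not affected. With one hall per arm, hall and arm remain confounded whatever is changed, so the fix reduces one source of bias but does not make the comparisons confirmatory. The conclusion assumes that the papers not supplied do not already settle these steps.

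**What to change.** Revise sections 5.5 and 10.1.1 as follows, with matching text in 3 and 9.

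1. Use one neutral card design and wording in both halls, leading to the same survey consent and baseline survey. Identify the hall through a link or code that does not look different, so that app access does not rest on self-reported hall.
2. Release the MKit code and an MKit-specific consent only on the baseline completion page, and only in the intervention hall. This makes 5.5 match 4.1.
3. In both arms, use students who complete consent and baseline as the retention denominator. Keep those who decline MKit in it. Assess usability and acceptability among those who signed up, and report how many did not.
4. Send both arms identical 1- and 5-month survey invitations and reminders, separate from the MKit goal alerts, from a contact file kept apart from survey and app-use data (10.1.3).
5. Report by hall the numbers given a card, consenting, completing baseline, signing up to MKit (intervention hall) and completing each follow-up. State that between-arm comparisons are descriptive because one hall per arm confounds hall with arm.

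**Cost.** Reprinted cards, an IRB change for the two-step consent, a contact file and automated reminders. Some app uptake will be lost between baseline and sign-up, though that loss is itself feasibility data. A few students may be deterred by giving contact details on a sensitive topic. Because addresses are not linked to responses, reminders will also reach students who have already answered.

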## 6 STUDY INTERVENTION

### 6.1 STUDY INTERVENTION ADMINISTRATION

#### 6.1.1 STUDY INTERVENTION DESCRIPTION

This study will test a web-based application focused on healthy relationships and sexual violence. The web-based application will provide information and resources using a life-skills approach. Participants will also have the opportunity to set personal goals, find resources, and evaluate their interpersonal relationships and self-care. This web-based application will have the ability to be utilized on any smartphone, tablet, laptop, or desktop computer.

#### 6.1.2 DOSING AND ADMINISTRATION

Intervention group participants will have five months to interact with the WebApp content, as this time period should present sufficient time for meaningful short-term change in the outcomes of interest. Further, the study will run for the duration of the school year, allowing study staff to follow students from the beginning of the school year to the end of the school year as they interact with the WebApp content. Study participants can choose to interact with the WebApp and take study surveys whenever is comfortable and safe for them to do so.

## 6.2 PREPARATION/HANDLING/STORAGE/ACCOUNTABILITY

### 6.2.1 ACQUISITION AND ACCOUNTABILITY

MKit was created through collaboration with students, stakeholders, and topical experts and developed by the Center for Health Communications Research (CHCR) through a modification of the pre-existing iCON platform. After development the management of the WebApp was transferred to Arbormoon Software, Inc. Arbormoon will maintain the WebApp servers throughout the entirety of the study.

### 6.2.2 FORMULATION, APPEARANCE, PACKAGING, AND LABELING

Not Applicable

### 6.2.3 PRODUCT STORAGE AND STABILITY

Not Applicable

### 6.2.4 PREPARATION

MKit was created through collaboration with students, stakeholders, and topical experts and developed by CHCR through a modification of the pre-existing iCON platform.

## 6.3 MEASURES TO MINIMIZE BIAS: RANDOMIZATION AND BLINDING

Study subjects will be randomized into one of two groups: 1) Intervention (WebApp and current prevention programming on campus) or 2) Control (current prevention programming on campus only), with 150 students in each group. We will use cluster-randomization by residence hall (to minimize contamination associated with individual-level randomization of students living in the same residence hall).

This study will not involve blinding.

## 6.4 STUDY INTERVENTION COMPLIANCE

Not Applicable

## 6.5 CONCOMITANT THERAPY

Not Applicable

### 6.5.1 RESCUE MEDICINE

Not Applicable

## 7 STUDY INTERVENTION DISCONTINUATION AND PARTICIPANT DISCONTINUATION/WITHDRAWAL

### 7.1 DISCONTINUATION OF STUDY INTERVENTION

All participation is voluntary. There is no penalty to anyone who decides not to participate or who wishes to end participation during the study. All participants may choose not to answer a question at any point in the study.

If a participant discontinues use of the intervention during the research study, their data will be retained for attrition analyses.

### 7.2 PARTICIPANT DISCONTINUATION/WITHDRAWL FROM THE STUDY

All participation is voluntary. There is no penalty to anyone who decides not to participate or who wishes to end participation during the study. All participants may choose not to answer a question at any point in the study. All participants may choose to withdraw from the study at any time.

If a participant withdraws from the research study, their data will be retained for attrition analyses.

### 7.3 LOST TO FOLLOW-UP

If a participant withdraws from the research study or is lost to follow-up, their data will be retained for attrition analyses.

## 8 STUDY ASSESSMENTS AND PROCEDURES

### 8.1 EFFICACY ASSESSMENTS

The efficacy of this study is not a primary outcome as this is a pilot study focused on safety, acceptability, usability, and willingness to use. However, a number of measures will be used to gather preliminary data for future scale-up at all three time points (baseline, 1-month, and 5-months). Study participants' knowledge, attitudes, and experiences will be measured with the following measures:

- 1) Investigator developed questions on knowledge about sexual and intimate partner violence (n=20) adapted from the Texas Education Program Participant Response Form ([https://www.wcasa.org/file\\_open.php?id=787](https://www.wcasa.org/file_open.php?id=787))
- 2) Investigator developed questions on self-efficacy (n=15)
- 3) 34 questions from the Revised Intimate Partner Violence Attitude Scale (Finchman, Cuit, Braithwaite, & Pasley, 2008)
- 4) Investigator developed questions on consensual sex (n=2)

- 5) 10 items from the Sexual Experiences Survey (SES) will measure past experiences with sexual violence (Koss et al., 2007) and 10 items from the Sexual Experiences Survey (SES) will measure past experiences with perpetration (Koss et al., 2007)
- 6) 26 questions from the Universal Violence Prevention Screening Protocol – Adapted questions (Heron, Thompson, Jackson, & Kaslow, 2003).

All of these are measures have been validated and used extensively in the United States to measure knowledge and attitudes related to gender based violence.

## 8.2 SAFETY AND OTHER ASSESSMENTS

The safety of MKit will be assessed through post-intervention semi-structured interviews, conducted with 25 participants including 15 participants from the intervention group and 10 participants from the control group.

## 8.3 ADVERSE EVENTS AND SERIOUS ADVERSE EVENTS

### 8.3.1 DEFINITION OF ADVERSE EVENTS (AE)

Adverse event means any untoward medical occurrence associated with the use of an intervention in humans, whether or not considered intervention-related (21 CFR 312.32 (a)).

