## 2.3 RISK/BENEFIT ASSESSMENT

### 2.3.1 KNOWN POTENTIAL RISKS

There is no more than minimal risk to the study subjects. There is a rare risk that a participant may experience emotional discomfort related to survey or semi-structured interview questions. All participants will receive resources to help alleviate any potential discomfort and will have the opportunity to skip any questions they choose. The rare possibility of breach of confidentiality exists. All data will be stored on a secure, HIPAA-compliant server and drive with monitored and controlled access to reduce this risk.

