### 8.3.4 TIME PERIOD AND FREQUENCY FOR EVENT ASSESSMENT AND FOLLOW-UP

The occurrence of an adverse event (AE) or serious adverse event (SAE) may come to the attention of study personnel during study visits and interviews of a study participant upon review by a study monitor.

All AEs including local and systemic reactions not meeting the criteria for SAEs will be captured on the appropriate case report form (CRF). Information to be collected includes event description, time of onset, clinician’s assessment of severity, relationship to study product (assessed only by those with the training and authority to make a diagnosis), and time of resolution/stabilization of the event. All AEs occurring while on study must be documented appropriately regardless of relationship. All AEs will be followed to adequate resolution.

Changes in the severity of an AE will be documented to allow an assessment of the duration of the event at each level of severity to be performed. AEs characterized as intermittent require documentation of onset and duration of each episode.

The Clinical Research Coordinator will record all reportable events with start dates occurring any time after informed consent is obtained until the last day of study participation. Events will be followed for outcome information until resolution or stabilization.

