### 8.3.5 ADVERSE EVENT REPORTING

The Primary Investigator will immediately report to the sponsor any adverse event, whether or not considered study intervention related, including breach of confidentiality or lack of safety whether there is a reasonable possibility that the study intervention caused the event. All adverse events (AEs) will be followed until satisfactory resolution or until the site investigator deems the event to be chronic or the participant is stable. Other supporting documentation of the event may be requested by the study sponsor and should be provided as soon as possible.

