## 8.4 UNANTICIPATED PROBLEMS

### 8.4.1 DEFINITION OF UNANTICIPATED PROBLEMS (UP)

The Office for Human Research Protections (OHRP) considers unanticipated problems involving risks to participants or others to include, in general, any incident, experience, or outcome that meets **all** of the following criteria:

- Unexpected in terms of nature, severity, or frequency given (a) the research procedures that are described in the protocol-related documents, such as the Institutional Review Board (IRB)-approved research protocol and informed consent document; and (b) the characteristics of the participant population being studied;
- Related or possibly related to participation in the research (“possibly related” means there is a reasonable possibility that the incident, experience, or outcome may have been caused by the procedures involved in the research); and
- Suggests that the research places participants or others at a greater risk of harm (including physical, psychological, economic, or social harm) than was previously known or recognized.

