#### 10.1.8 QUALITY ASSURANCE AND QUALITY CONTROL

The investigators will perform internal quality management of study conduct, data, documentation, and completion.

Any study problems with MKit, including any problems with the study and surveys, communicated through the study email address ([[contact]](mailto:[contact])) by study participants, will be addressed by the study team in a timely fashion.

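### The adverse-event definition does not match the protocol's own named risks, and 275 of 300 students have no scheduled contact at which harm from taking part is asked about

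*Combined protocol and SAP*

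**What the plan says.** Section 2.3.1 names two risks. The first is emotional: "There is a rare risk that a participant may experience emotional discomfort related to survey or semi-structured interview questions". The second concerns privacy: "The rare possibility of breach of confidentiality exists".

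Section 8.3.1 defines the events to be captured: "Adverse event means any untoward medical occurrence associated with the use of an intervention in humans, whether or not considered intervention-related". Section 8.3.3.2 then grades causality only against the study intervention.

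Section 8.3.5 requires immediate reporting to the sponsor of any adverse event, "including breach of confidentiality or lack of safety". No part of section 8.3 mentions emotional discomfort.

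On how events are found, 8.3.4 says that they "may come to the attention of study personnel during study visits and interviews of a study participant upon review by a study monitor". The schedule in 1.3 lists a baseline survey, 1-month and 5-month surveys, and post-study interviews. Perceived safety appears only in the interview column. Sections 8.2, 9.4.2 and 9.4.4 base the safety assessment on 25 interviews (15 intervention, 10 control). Section 5.5 says that the invitation to these interviews is on the final page of the 5-month survey.

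**The concern.** Safety is one of the primary endpoints (sections 1.1 and 3), and 9.4.1 says the results will establish it for future scale-up. The harms most plausible in this study are not medical. They are upset caused by questions about sexual violence, and loss of privacy. A definition borrowed from drug regulation does not clearly capture the first, and it disagrees with the reporting clause on the second. Staff applying the text could reasonably differ on whether to log the same event.

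The way events are found adds to the problem. If nobody asks most students about harm, the few reports that arrive depend on who chooses to write in. The interviews, which carry the safety endpoint, draw only on students who reached the end of the last survey. Safety would then be judged mainly from those least likely to have left because of distress.

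**Working it through.** The documents give no figure for this point. The check is a comparison of sections, a count, and one illustration.

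**1. Named risks against the definition.**
- *Emotional discomfort from questions (2.3.1).* The definition needs a medical occurrence associated with use of an intervention. Discomfort caused by a questionnaire is not plainly medical and does not arise from using MKit. Distress needing care might be judged medical, so coverage is unclear and not certainly absent. Section 8.3.3.2 has no category for an event caused by the surveys or interviews.
- *Breach of confidentiality (2.3.1).* It is not a medical occurrence, so it lies outside 8.3.1. Section 8.3.5 nevertheless lists it among reportable adverse events. The two sections disagree.

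**2. Whether the unanticipated-problem rules fill the gap.** Section 8.4.1 does mention "greater risk of harm (including physical, psychological, economic, or social harm) than was previously known or recognized". It requires all three of its criteria, including that the event be unexpected and point to a risk greater than already known. Discomfort is already listed in 2.3.1, so ordinary discomfort would normally fail both of these.

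**3. Who is asked about harm.** Inputs: 300 students, 150 per arm (1.1); 15 + 10 = 25 interviewed (8.2).
- Not interviewed: 300 − 25 = 275; 275/300 = 91.7%.
- By arm: 150 − 15 = 135 intervention; 150 − 10 = 140 control.

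The surveys at 1 and 5 months repeat the baseline measures and add usability and acceptability scales in the intervention arm (4.1). The victimization and partner-violence scales measure outcomes; they do not ask whether taking part caused harm. So 275 is the number with no scheduled contact at which such harm is asked about.

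**4. What the interviews can show.** The documents give no harm rate, so rates of 1%, 2% and 5% are assumed. The chance that at least one affected student is among n is 1 − (1 − p)^n.

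| Assumed rate p | n = 15 (intervention interviewees) | n = 150 (whole intervention arm) |
|---|---|---|
| 1% | 1 − 0.99^15 = 14% | 1 − 0.99^150 = 78% |
| 2% | 1 − 0.98^15 = 26% | 1 − 0.98^150 = 95% |
| 5% | 1 − 0.95^15 = 54% | 1 − 0.95^150 = over 99.9% |

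If no event is seen, the one-sided 95% upper limit is 1 − 0.05^(1/n): 18.1% for n = 15 and 2.0% for n = 150.

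The n = 15 column treats interviewees as a random sample. They are volunteers who completed the 5-month survey and were chosen by level of MKit use (5.5). The n = 150 column assumes that everyone answers. Sections 7.1 to 7.3 keep leavers' data for attrition analyses but describe no collection of reasons for leaving.

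**The case against.** Several stronger readings are tempting, and the documents do not support them.

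- *A breach of confidentiality escapes adverse-event handling.* It does not. Section 8.3.5 covers events "including breach of confidentiality or lack of safety whether there is a reasonable possibility that the study intervention caused the event". The defect is inconsistency with 8.3.1, not omission.
- *The 275 students cannot report harm.* They can. Section 10.1.8 says the team will address "Any study problems with MKit, including any problems with the study and surveys, communicated through the study email address", and every student is due two follow-up surveys. The consent forms listed in 10.1.1.1 are not in the text available for review and may give further routes. The email is a passive route, though. It is described under quality control and is not tied to the adverse-event form.
- *Control-arm harms are excluded.* No rule in section 8.3 is limited to one arm. Section 8.3.4 requires events while on study to be documented regardless of relationship. What remains is that 8.3.1 and 8.3.3.2 are framed around an intervention that control students do not use.
- *A low adverse-event count will be taken as proof that MKit is safe.* Section 9 plans no adverse-event count or rate. The safety endpoint is the interviews.

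It can also be said that this is a minimal-risk study with rare named risks, that the definition is a standard one, and that students receive resources and may skip questions. Those points limit the urgency. They do not reconcile the sections or create a question about harm. A last objection is practical and stands: 10.1.3 bars linking survey data to identity, so a bare survey item would yield events that staff could not follow to resolution as 8.3.4 requires. The change has to provide for that.

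**Conclusion.** The point holds as a mismatch and an ascertainment gap. Section 8.3.1 does not fit the risks in 2.3.1 or the reporting clause in 8.3.5, and 8.3.4 relies on visits that are not scheduled. For 275 of 300 students (91.7%), a harm is recorded only if they volunteer it. The safety endpoint rests on 25 interviewees, 15 of them from the MKit arm, and students who left before the end of the 5-month survey because of distress cannot be among them.

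The count assumes full enrolment and that all 25 interviews take place. The detection figures rest on assumed harm rates and random sampling; they show scale only. It does not follow that students lack any means of reporting, or that the plan intends to infer safety from an event count. The change should be made because safety is a primary endpoint and surveys that both arms already receive can carry the question.

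**What to change.** 1. Reconcile 8.3.1, 8.3.3.2 and 8.3.5 with 2.3.1, so that psychological, social and privacy-related events linked to MKit, the surveys or the interviews count in either arm.
2. In 8.3.4, replace the study visits with the contacts that exist: the follow-up surveys (once they carry the question below), the study email and the interviews.
3. Add one question to the 1- and 5-month surveys in both arms, asking whether taking part caused upset, a privacy problem or trouble with another person. Report the counts by arm alongside the interview findings.
4. Show the study email or an optional contact field beside the question, so that an event can be followed up without linking the rest of the survey to identity (10.1.3).
5. State how minor events reported by survey fit the immediate-reporting rule in 8.3.5.

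The cost is protocol wording, one survey item at two waves, a small change to survey and consent wording, and more minor events to log. The survey question cannot reach students who stop answering, so the counts should be shown with the number responding in each arm.
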